3.1.1 Cross-over

Patients who develop disease-progression or unacceptable treatment-related toxicity on either sunitinib or everolimus will cross-over to the other drug.

Patients must start cross-over within 3 months of discontinuation of the first line of treatment. Unacceptable toxicity must have resolved to CTCAE Grade 1 or baseline.

Before cross-over eligibility must be confirmed (tests do not need to be repeated if they have already been performed within the required timeframe):

Within 4 weeks prior:

- CT C/A/P or MRI

Within 2 weeks prior:

[figure not shown]
- Physical examination including weight, vital signs and ECOG status
- Laboratory Evaluations
 - CBC with differential and platelets
 - Chemistries: Sodium (Na), Potassium (K), Chloride (Cl), Total CO₂ (bicarbonate), Creatinine, Glucose, Urea nitrogen (BUN), Albumin, Calcium total, Alkaline Phosphatase, ALT/GPT, AST/GOT, Total Bilirubin, Total Protein

During cross-over treatment patients will have regular study assessments as described in Study Calendar [Error! Reference source not found.](#)

3.1.2 Long term follow up

After discontinuation from the study, the subjects will be contacted at 3 months intervals to obtain information about subsequent treatment(s) and survival status by phone or e-mail.

Figure 2. Study flow chart and treatment selection based on tumor genotype.

CR-complete response, PR-partial response, SD-stable disease, PD-disease progression

Treatment will continue until disease progression, unacceptable treatment-related toxicity, or consent withdrawal. Response to treatment (CR/PR/SD) will be assessed using RECIST v1.1 (See Section 6.3) every 3 months after initiation of treatment.

3.2 STUDY DRUG ADMINISTRATION

3.2.1 Sunitinib Treatment and dose

Patients on Arm 1 will be treated with oral sunitinib at a starting dose of 37.5 mg once daily.

Patients will take sunitinib once daily in the morning, with or without food, as desired. Patients should be advised to drink plenty of water or take rehydration fluids to avoid dehydration if

diarrhea occurs. If a dose is missed the subject will be instructed to take the next dose as scheduled.

- 3.2.1.1 Because hypertension is a known and potentially serious adverse event associated with sunitinib maleate treatment, patients will have their blood pressure monitored and recorded at baseline and weekly during sunitinib treatment either at the doctor's office or using any calibrated electronic device (such as those found at a local drug store or pharmacy). **Appendix E** detail the collection and recording of blood pressure related information.
- 3.2.1.2 Patients with bulky solid tumors should be monitored closely for pneumothorax, intestinal fistulae, or intestinal perforation in the event of rapid tumor destruction.
- 3.2.1.3 Patients should be alerted to the possibility that sunitinib capsules can cause a yellow discoloration of the skin on direct contact. If this happens, the patient should wash immediately with soap and water.
- 3.2.1.4 Thyroid function (free T4, T3 and TSH) will be monitored at every cycle).

3.2.2 Everolimus Treatment and dose

Patients on Arm 2 will be treated with oral everolimus at a starting dose of 10 mg once daily.

The tablets should be swallowed whole with a glass of water and should not be chewed or crushed. For patients unable to swallow tablets, the tablet(s) should be dispersed completely in a glass of water (containing approximately 30 mL) by gently stirring until the tablet(s) is fully disintegrated (approximately 7 minutes), immediately prior to drinking. The glass should be rinsed with the same volume of water and the rinse completely swallowed to ensure the entire dose is administered.

If vomiting occurs, no attempt should be made to replace the vomited dose. Patients should be instructed that if they miss a dose on one day, they must not take any extra dose the next day, but instead to immediately contact the study center as soon as possible to ask for advice.

Table 3. Choice of targeted therapy driven by the findings of the precise molecular alterations based on common mutations that occur in NETs.

Study Agent	Mutations *	Affected Pathways	
Everolimus	PTEN	PI3K/AKT/mTOR	
	PI3K	PI3K/AKT/mTOR	
	AKT	PI3K/AKT/mTOR	
	mTOR	PI3K/AKT/mTOR	
	VHL	Hypoxia induced PI3K/AKT/mTOR	
	TSC1	PI3K/AKT/mTOR	
	TSC2	PI3K/AKT/mTOR	
	NF1	TSC2/mTOR , Hypoxia induced neoangiogenesis	
Sunitinib	MEN1	Cell growth, cell cycle and genome instability	
	FLT3	Cell survival, proliferation, and differentiation	
	PDGFR	Cell proliferation, cell migration, neoangiogenesis	
	ATM		
	KIT	Cell survival, proliferation, and differentiation	
	ATRX	Cell survival, proliferation, and differentiation	

*Mutations in genes not listed above or that are wildtype will be treated with sunitinib (see [Appendix C](#) for list of other genes that will be genotyped). Germline DNA will be obtained for comparison to tumor genotype data for every patient. Also, some patients with known familial cancer syndromes (*MEN1* and *VHL*) will be included in the study and tumor biopsy for the sole purpose of agent selection in these patients will not be performed.

3.2.3 CCR Self-Administered Study Drugs Policy

All oral self-administered investigational agents will be properly accounted for, handled, and disposed in accordance with existing federal regulations and principles of Good Clinical Practice. All oral study drugs will be recorded in the patient diary found in [Appendix F](#). This will be used as a memory aide for subjects. The clinical research team will maintain the primary source record.

Subjects should be asked to bring the diary as well as unused study agent and empty containers with them at each study visit. If a subject goes off study while at home, the research nurse will ensure and document the return of the unused oral investigational agents from the participant.

Unused investigational study agents will be disposed and destroyed per CC pharmacy SOPs.

3.3 DOSE MODIFICATIONS/DOSE DELAY

Patients are allowed to remain off treatment for up to 12 weeks.

Patients requiring >12 weeks of study medication dose interruption due to persistent toxicity will be either crossed over to the other arm or discontinued from the treatment.

3.3.1 Sunitinib

Subjects experiencing severe toxicity (see dose modification [Table 5](#) below) will have 1-week treatment rests inserted into the regimen as needed and may dose reduce depending on individual

tolerability. The dose of 37.5 mg may be reduced to 25 mg daily, which is the minimum dose acceptable for daily dosing of sunitinib. Intra-patient re-escalation of study medication back to previous dose is permitted at the discretion of the investigator and considering the patient's clinical status.

Subjects not experiencing a response by RECIST criteria and experiencing only Grade ≤ 1 non-hematological or Grade ≤ 2 hematological toxicity within the first 8 weeks of treatment may dose escalate to 50 mg daily at any time after 8 weeks. If dose is escalated or reduced, treatment will continue to be on a continuous daily dosing schedule.

The doses of study medication may be modified as outlined in **Table 4**.

Table 4: Sunitinib Dose levels

Dose Level	Daily Dose	Dispensed As
-1	25 mg*	1 x 25 mg capsule or 2 x 12.5 mg capsule
0 (Starting Dose Level)	37.5 mg	3 x 12.5 mg capsule
+1	50 mg	1 x 50 mg capsule or 2 x 25 mg capsules)
*Patients will not be treated at less than 25 mg per day. If a dose reduction is required at this level, the subject will be removed from study therapy		

Inpatient dose reduction by 1 dose level (to 25 mg/day, or to 37.5 mg/day if the subject has been receiving 50 mg/day) may be required depending on the type and severity of toxicity encountered. In **Table 5** is an outline of the recommended dose modifications for study treatment-associated toxicity that will be used in this protocol.

Table 5. Dose Modifications for Sunitinib - Associated Toxicity

Toxicity	Grade 1/2 ¹	Grade 3	Grade 4
Hypertension	See Table 6	See Table 6	See Table 6
Other Non-hematologic	Continue at the same dose level.	
 Withhold dose until toxicity is Grade ≤ 1 or has returned to baseline, then resume treatment at the same dose level. If the toxicity recurs with Grade 3 severity (except hepatotoxicity), at the discretion of the investigator, reduce the dose by 1 level. If ASL/ALT or bilirubin elevation recurs with grade 3 severity, the patient will be removed from the study. 	Withhold dose until toxicity is Grade ≤ 1 or has returned to baseline, then reduce the dose by 1 level and resume treatment, or discontinue at the discretion of the investigator

Toxicity	Grade 1/2 ¹	Grade 3	Grade 4
Hematologic	Continue at the same dose level.	Withhold dose until toxicity is Grade ≤ 2 or has returned to baseline, then resume treatment at the same dose level ² . If the toxicity recurs with Grade 3 severity, at the discretion of the investigator, reduce the dose by 1 level	Withhold dose until toxicity is Grade ≤ 2 or has returned to baseline, then reduce the dose by 1 level and resume treatment ²

¹If after the first 8 weeks there is no response according to RECIST and toxicity remains \leq non-hematological Grade 1 or \leq hematological Grade 2 dose escalation to 50 mg/day may be considered.

² Patients who develop grade 4 hyperuricemia or grade 3 hypophosphatemia without clinical symptoms may continue study treatment without interruption at the discretion of the investigator. Nausea, vomiting, or diarrhea must persist at grade 3 or 4 despite maximal medical therapy. Patients who develop Grade 3 or 4 lymphopenia may continue study treatment without interruption. Complicated neutropenia includes duration of Grade 4 longer than 7 days or concurrent fever or infection.

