2.1 ELIGIBILITY CRITERIA

2.1.1 Inclusion Criteria

- 2.1.1.1 Progressive, histologically or cytologically diagnosed low or intermediate grade, neuroendocrine tumors confirmed by the Laboratory of Pathology, NCI or a pathology laboratory at the enrolling institution. Disease progression is defined according to RECIST criteria for progression of disease (see Section 6.3) or any new lesions seen on 68-Gallium DOTATATE within 18 months prior to enrolment (per PI discretion and if 68-Gallium DOTATATE is performed at the enrolling institution).
- 2.1.1.2 Age \geq 18 years, because the incidence and prevalence of metastatic pancreatic and gastrointestinal neuroendocrine tumors in the pediatric patient population is exceedingly rare (children are excluded from this study, but will be eligible for future pediatric trials).
- 2.1.1.3 Patients must have measurable disease according to RECIST criteria (see Section 6.3) on anatomic imaging studies (CT scan or MRI).
- 2.1.1.4 Willingness to undergo tumor biopsy if the patient does not have a known familial cancer syndrome (MEN1, VHL and NF1) or archival tissue available.
- 2.1.1.5** ECOG performance status <2 (see **Appendices**
- 2.1.1.6 **Appendix A**).
- 2.1.1.7 Patients must have normal organ and bone marrow function as defined below:

- hemoglobin \geq 9 g/dL*
 - leukocytes \geq 3,000/mcL*
 - absolute neutrophil count \geq 1,500/mcL*
 - platelets \geq institutional lower limit of normal*
 - total bilirubin within normal institutional limits
 - AST(SGOT)/ALT(SGPT) \leq 2.5 X institutional upper limit of normal (\leq 5 x ULN in patients with liver metastases)
 - creatinine within normal institutional limits
- OR
- creatinine clearance \geq 60 mL/min/1.73 m² for patients with creatinine levels above institutional normal.
 - INR \leq 2;

*If a patient's bone marrow function falls below the indicated values and it is not thought to be related to prior treatments a hematology consult will be ordered. If Hematology deems the patients safe to proceed with treatment they will be allowed to enroll on study. In such cases, the patient's absolute neutrophil count must be $>$ 1,000/mcL, hemoglobin must be $>$ 7.5 g/dL and the platelet count must be $>$ 75,000 mcL. Each patient will also be seen by a medical oncologist at follow-up visits if possible.

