2.3 REGISTRATION PROCEDURES

Authorized staff must register an eligible candidate with NCI Central Registration Office (CRO) within 24 hours of signing consent. A registration Eligibility Checklist from the web site (<http://home.ccr.cancer.gov/intra/eligibility/welcome.htm>) must be completed and sent via encrypted email to: NCI Central Registration Office [contact]. After confirmation of eligibility at Central Registration Office, CRO staff will call pharmacy to advise them of the acceptance of the patient on the protocol prior to the release of any investigational agents. Verification of Registration will be forwarded electronically via e-mail to the research team. A recorder is available during non-working hours.

2.3.1 Treatment Assignment Procedures (For registration purposes only):

Cohorts

Number	Name	Description
1	Cohort 1	Subjects with wild type NETs or mutations in MEN1/PDGFR/KIT/FLT3 or mutations not known to be specifically targeted by sunitinib or everolimus
2	Cohort 2	Subjects with NETs and mutations in NF1/PTEN/PI3K/AKT/mTOR/VH/TP53L but not in MEN1/PDGFR/KIT/FLT3

Arms

Number	Name	Description
1	Arm 1	Sunitinib
2	Arm 2	Everolimus

Arms Assignments

Subjects in Cohorts 1 will be directly assigned to Arm 1.

Subjects in Cohorts 2 will be directly assigned to Arm 2.

Subjects who develop disease progression or unacceptable treatment-related toxicity during treatment in either Arm 1 or Arm 2 will cross-over to the other Arm.

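### Table 5 takes sunitinib patients with recurrent grade 3 liver-test elevation off the study, although the protocol's other rules allow cross-over or take them off therapy only

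*Combined protocol and SAP*

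**What the plan says.** In Table 5 (section 3.3.1), the grade 3 cell for other non-hematologic toxicity withholds sunitinib until recovery and then resumes it at the same dose. If the toxicity recurs at grade 3, the investigator may reduce the dose, but hepatotoxicity is excepted and has its own rule: "If ASL/ALT or bilirubin elevation recurs with grade 3 severity, the patient will be removed from the study".

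The cross-over rule appears twice. Section 2.3.1 states: "Subjects who develop disease progression or unacceptable treatment-related toxicity during treatment in either Arm 1 or Arm 2 will cross-over to the other Arm". Section 3.1.1 repeats it and adds conditions: "Unacceptable toxicity must have resolved to CTCAE Grade 1 or baseline"; "Patients must start cross-over within 3 months of discontinuation of the first line of treatment"; "Before cross-over eligibility must be confirmed". The chemistries due in the 2 weeks before cross-over include ALT, AST and total bilirubin.

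Section 3.5 separates two statuses. Unacceptable toxicity, with a pointer to section 3.3, is listed in 3.5.1 as a reason to come off protocol therapy. The off-study list in 3.5.2 has participant request, loss to follow-up, investigator discretion, screen failure, death and closure by the principal investigator. Toxicity is not on it. Section 3.5.3 requires the registration office to be told of each status.

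**The concern.** Stopping sunitinib for good here is not in question. The boxed warning in 11.1.2 advises against restarting it after later severe changes in liver tests. The difficulty is what happens to the patient next. A site that follows Table 5 takes the patient off study. A site that follows 3.1.1 checks for recovery and starts everolimus. A site that follows 3.5.1 ends protocol therapy and keeps the patient in the study.

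At stake is on-protocol access to the second drug for a patient whose liver tests have recovered. A secondary matter is whether safety collection could stop early because the patient has been recorded as off-study.

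**Working it through.** No power or sample-size calculation applies. The check sets the rules side by side for one patient: on first-line sunitinib, a grade 3 ALT rise, recovery, resumption, a second grade 3 rise, then recovery again.

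1. Disposition under each rule.

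| Rule | Outcome for this patient |
|---|---|
| Table 5 | Off study, automatically |
| 2.3.1 and 3.1.1 | Everolimus, if recovered, eligible and started in time |
| 3.5.1 | Off protocol therapy, with a 30-day safety visit |
| 3.5.2 | No listed criterion met, short of investigator discretion |

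2. Wording of comparable stopping rules. Table 4 (sunitinib minimum dose), Table 7 (everolimus minimum dose) and the notes to Table 6 (hypertension) all end study or protocol therapy. None ends study participation. The Table 5 liver rule departs from that pattern.

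3. Who loses something. Only a patient who would meet the 3.1.1 conditions loses cross-over. Recovery to grade 1 is not sufficient, because eligibility under 2.1.1.7 also applies. It requires "total bilirubin within normal institutional limits" and AST/ALT at most 2.5 times the upper limit of normal (5 times with liver metastases). Table 8 shows grade 1 AST/ALT reaching 3.0 times that limit, so without liver metastases a grade 1 value between 2.5 and 3.0 counts as resolved but not as eligible. Table 5 also governs patients who reached sunitinib by crossing over from everolimus; they have no second drug left to lose.

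4. What off-study status could switch off. Section 6.1 allows adverse-event follow-up to end at off-study, and 7.3.1 and 7.3.2 have similar limits for serious events. Against that:
   - 6.1 also has all adverse events followed to baseline or stabilization.
   - 3.5.1 requires the 30-day visit in every case of removal from therapy, and the calendar in 3.4 includes chemistries at that visit.
   - 7.3.2 keeps serious events suspected to be related to sunitinib reportable with no time limit.
   - 3.1.2 keeps 3-monthly survival contact after a patient discontinues the study.

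5. Size. The documents give no rate of recurrent grade 3 liver tests on sunitinib, so no patient count is estimated. Section 8 aims for 44 evaluable patients per arm under a ceiling of 120. If both arms reach 44, first-line sunitinib has between 44 and 120 − 44 = 76 patients. One patient is then 1/76 = 1.3% to 1/44 = 2.3% of the arm. The only overall hepatic frequency in 11.1.2 is liver failure, 7/2281 = 0.3%, which is a different event and serves only as context.

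**The case against.** The strongest defence is that Table 5 makes a deliberate liver exception. The preceding bullet excepts hepatotoxicity by name, so liver events were singled out on purpose. Barring cross-over could also be medically coherent: everolimus raises transaminases and bilirubin (4.1.2), has its own AST/ALT stopping rules (Table 8) and needs lower doses in hepatic impairment (3.3.2.1). What stands is that a sponsor could reasonably choose this. But the named exception is from dose reduction and says nothing about cross-over, and neither 2.3.1 nor 3.1.1 carries it. It also sits oddly beside the grade 4 cell of the same row, which allows the investigator to "then reduce the dose by 1 level and resume treatment, or discontinue at the discretion of the investigator".

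A second defence is that the protocol uses study language loosely. Section 3.1.2 speaks of discontinuation from the study for patients who are still contacted every 3 months. That stands, and it weakens any claim that survival data would be lost. It does not restore cross-over. Likewise, the 3.5.2 list need not be exhaustive and includes investigator discretion, but discretion is case by case and Table 5 is automatic.

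Three stronger readings are tempting and not supported:

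- A reader might infer a direct conflict with section 3.3, under which patients "will be either crossed over to the other arm or discontinued from the treatment". That rule is triggered only by an interruption of more than 12 weeks, whereas Table 5 is triggered by recurrence after resumption. It is supporting context: leaving the study is not among the outcomes 3.3 gives for toxicity.
- A reader might infer that liver-toxicity patients would go unfollowed. The provisions in step 4 of the working largely prevent that.
- A reader might infer bias in first-line PFS. A patient who crosses over before progression does keep 3-monthly scans, but no event rate is given from which to size an effect, and the power calculation does not use this rule.

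**Conclusion.** Wrong as written, and minor. The Table 5 instruction contradicts the cross-over rule in 2.3.1 and 3.1.1 and the off-therapy/off-study split in 3.5.1 and 3.5.2. Its concrete consequence is that a recovered, eligible first-line sunitinib patient could be denied everolimus on protocol. Early closure of safety collection is possible on a literal reading, but other text mostly covers it.

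Few patients are likely to be affected, though that is a judgement and not an estimate. The 1.3% to 2.3% per patient assumes both arms reach 44 under the ceiling of 120 and counts evaluable patients only. The conclusion on the conflict itself rests on the text and on no numerical assumption.

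**What to change.** Replace the liver sentence in Table 5 with wording to this effect, and correct ASL to AST:

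*Sunitinib will be permanently discontinued. A patient on first-line sunitinib may cross over to everolimus if all 3.1.1 conditions are met: toxicity resolved to grade 1 or baseline, eligibility re-confirmed including the liver criteria in 2.1.1.7, and cross-over started within 3 months of stopping sunitinib. Otherwise, and for any patient already crossed over from everolimus, the patient goes off protocol therapy and into follow-up.*

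If the sponsor intends to bar cross-over after recurrent liver toxicity, write that exception into 2.3.1 and 3.1.1 and still use off protocol therapy in Table 5. Section 6.1 needs no change.

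The cost is amendment wording in one table cell, plus a sentence in each of 2.3.1 and 3.1.1 only if an exception is wanted. No visits or tests are added, because the pre-cross-over checks and the 30-day visit are already in the protocol.

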AST or ALT elevation Grade 3 (> 5.0 - 20.0 ULN)*	Interrupt everolimus administration until resolution to \leq grade 1 (or \leq grade 2 if baseline values were within the range of grade 2). If resolution occurs within ≤ 7 days, everolimus should be re-started at the dose level prior to interruption. If resolution takes > 7 days, or if event reoccurs within 28 days, hold everolimus until recovery to \leq grade 1 or baseline grade / value and reintroduce everolimus at one dose level lower. .
AST or ALT elevation Grade 4 (> 20 x ULN)*	Interrupt everolimus administration until resolution to \leq grade 1 (or \leq grade 2 if baseline values were within the range of grade 2). If resolution occurs within ≤ 7 days, everolimus should be re-started at one dose level lower. If resolution takes > 7 days, discontinue everolimus.

Toxicity	Action
Intolerable grade 2 mucositis, or grade 3 AE, except hyperglycemia or hypertriglyceridemia or hypercholesterolemia (see Section 4.1.2.6)	Interrupt everolimus administration until resolution to \leq grade 1 or baseline grade / value. If resolution occurs within \leq 7 days, everolimus should be re-started at the dose level prior to interruption. If resolution takes $>$ 7 days, or if event reoccurs within 28 days, hold everolimus until recovery to \leq grade 1 or baseline grade / value and reintroduce everolimus at one dose level lower.
Any other grade 4	Hold everolimus until recovery to grade \leq 1 or baseline value Reintroduce everolimus at one dose level lower, if available.
Grade 3 or 4 clinical liver failure (asterixis or encephalopathy/coma)	Discontinue everolimus
Recurrence of intolerable grade 2 mucositis or grade 3 event after dose reduction	Reduce dose to the next lower dose level, if available. The lowest possible dose level of everolimus is 2.5 mg daily. Below this level, everolimus must be discontinued. If toxicity recurs at Grade 3, consider discontinuation
Recurrence of grade 4 after dose reduction	Discontinue everolimus
Any non-hematologic toxicity requiring everolimus interruption for $>$ 28 days	Discontinue everolimus
* Should HCV flare be confirmed, the guidelines for flare must take precedence (4.1.2.10)	

Table 9 Dosing guidelines for Everolimus-related hematologic toxicities

Toxicity	Action
Grade 2 thrombocytopenia (platelets <75, ≥ 50x10 ⁹ /L)	No action

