11.1.2 Toxicity

(Please see package insert for a complete list of toxicities)

In over 10,000 subjects with solid malignant tumors diarrhea (52.4%), fatigue (49.0%), nausea (42.7%), decreased appetite (38.5%), vomiting (33.9%), palmar-plantar erythrodysesthesia syndrome (28.7%), hypertension (27.6%), stomatitis (26.0%), dysgeusia (25.9%), and mucosal inflammation (25.7%) were the most commonly reported treatment emergent adverse events.

Overall, 60.3% experienced treatment-related AEs of Grade 3, 4, or 5 severity; Grade 3 in 46.9% of subjects, Grade 4 and grade 5 in 11.9% and 1.6% of subjects respectively. The most commonly reported were neutropenia (13.5%), fatigue (9.2%), thrombocytopenia (8.6%), palmar-plantar erythrodysesthesia syndrome (7.4%), diarrhea (6.3%), hypertension (5.5%), and asthenia (5.0%).

Neutropenia (0.3%), fatigue (8.8%), palmar-plantar erythrodysesthesia syndrome (7.4%), thrombocytopenia (6.8%), diarrhea (6.1%); and hypertension (5.4%) were the most commonly reported treatment-related AEs of Grade 3 severity. Neutropenia (3.2%), thrombocytopenia (1.8%), and anemia (0.9%) were the most commonly reported treatment-related AEs of Grade 4 severity. Pulmonary embolism, cardiac failure, death, cerebral hemorrhage, renal failure, myocardial infarction, hepatic failure, gastrointestinal hemorrhage, multi-organ failure, respiratory failure, pneumonia, septic shock, cardiac arrest, sepsis, sudden death, tumor hemorrhage, and hemorrhage, were among the Grade 5 treatment-related AEs reported in at least 3 subjects.

Boxed Warning:

SUTENT has been associated with hepatotoxicity, which may result in liver failure or death. Liver failure has been observed in clinical trials (7/2281 [0.3%]) and post-marketing experience.

Liver failure signs include jaundice, elevated transaminases and/or hyperbilirubinemia in conjunction with encephalopathy, coagulopathy, and/or renal failure. Monitor liver function tests (ALT, AST, bilirubin) before initiation of treatment, during each cycle of treatment, and as clinically indicated. SUTENT should be interrupted for Grade 3 or 4 drug-related hepatic adverse events and discontinued if there is no resolution. Do not restart SUTENT if patients subsequently experience severe changes in liver function tests or have other signs and symptoms of liver failure.

Safety in patients with ALT or AST $>2.5 \times$ ULN or, if due to liver metastases, $>5.0 \times$ ULN has not been established.

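### Sunitinib Table 5 makes stopping mandatory when a liver-test elevation recurs at Grade 3 but optional when it recurs at Grade 4 on 37.5 or 50 mg, at odds with the natural reading of section 11.1.2

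*Combined protocol and SAP*

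**What the plan says.** Section 3.3.1, Table 5, handles liver-test elevations in the row for other non-hematologic toxicity.

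- **Grade 3 cell.** Hold sunitinib until the event settles, then resume at the same dose. If a Grade 3 toxicity recurs, the dose may be cut by one level, but hepatotoxicity is excluded from that option. For the liver tests the rule is: "If ASL/ALT or bilirubin elevation recurs with grade 3 severity, the patient will be removed from the study".
- **Grade 4 cell.** Hold until the event settles, "then reduce the dose by 1 level and resume treatment, or discontinue at the discretion of the investigator". The cell has no exception for the liver and does not mention recurrence.
- **Floor.** The Table 4 footnote sets 25 mg as the lowest dose: "If a dose reduction is required at this level, the subject will be removed from study therapy".
- **Re-escalation.** "Intra-patient re-escalation of study medication back to previous dose is permitted at the discretion of the investigator".

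The boxed warning in section 11.1.2 covers two stages. For the event itself: "SUTENT should be interrupted for Grade 3 or 4 drug-related hepatic adverse events and discontinued if there is no resolution". For what follows: "Do not restart SUTENT if patients subsequently experience severe changes in liver function tests or have other signs and symptoms of liver failure".

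**The concern.** Table 5 limits its only mandatory liver stop to recurrence at Grade 3. A recurrence at Grade 4 falls under the Grade 4 column, where stopping is one of two options. The severity order is inverted: the less severe recurrence has the stricter rule, and no reason is given.

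The stake is participant safety. Sites turn to the dosing table when an event occurs. An investigator who follows it without also checking 11.1.2 could give sunitinib again after a severe liver-test elevation has already come back on rechallenge. Sunitinib is the default arm for wild-type tumors, untargeted mutations and multiple mutations (2.3.1, 3.1), and everolimus patients cross over to it (3.1.1), so many participants come under this table.

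Table 5 also has no stop for liver failure, whereas everolimus Table 8 (3.3.2.3) has a row that discontinues for Grade 3 or 4 clinical liver failure. Read alone, the Grade 3 cell of Table 5 would return a patient with Grade 3 liver failure to the same dose after resolution.

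**Working it through.** The plan has no figure to reproduce. The check follows the Table 5 rules through a first and a second AST/ALT or bilirubin elevation.

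**Rules used (3.3.1, Tables 4 and 5)**

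1. First event Grade 3: resume at the same dose.
2. First event Grade 4: resume one level lower (50 to 37.5 mg, or 37.5 to 25 mg) or stop. The trace assumes that the resume option is taken.
3. A reduction required at 25 mg ends therapy.
4. Recurrence at Grade 3: removal.
5. Recurrence at Grade 4: one level lower, or stop, at discretion.

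The column is chosen by the grade of the current event, so a Grade 3 recurrence meets rule 4 whatever the grade of the first event.

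| First event | Dose at recurrence | Recurs at Grade 3 | Recurs at Grade 4 |
|---|---|---|---|
| 25 mg, Grade 3 | 25 mg | must stop | therapy ends (floor) |
| 25 mg, Grade 4 | therapy has ended | – | – |
| 37.5 mg, Grade 3 | 37.5 mg | must stop | may resume at 25 mg |
| 37.5 mg, Grade 4 | 25 mg | must stop | therapy ends (floor) |
| 50 mg, Grade 3 | 50 mg | must stop | may resume at 37.5 mg |
| 50 mg, Grade 4 | 37.5 mg | must stop | may resume at 25 mg |

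**Count.** 3 doses × 2 first grades = 6 starting cases. One ends at the first event, so 6 − 1 = 5 recurrence paths.

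- Grade 3 recurrence: stop mandatory in 5 of 5.
- Grade 4 recurrence: restart open in 1 of 1 at 50 mg, 2 of 2 at 37.5 mg and 0 of 2 at 25 mg, so 1 + 2 + 0 = 3 of 5.

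**Reachability.** A patient who starts at 37.5 mg and is never escalated or re-escalated has one open sequence: Grade 3, resume 37.5 mg, Grade 4, resume 25 mg. The other two need prior escalation to 50 mg. If a patient on a 25 mg path is re-escalated to 37.5 mg before the second event, as 3.3.1 allows, that path opens too.

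**Against 11.1.2.** A first Grade 4 event that resolves may be followed by a restart under both texts. A second, Grade 4 elevation after restart is, in the natural sense of the words, a subsequent severe change. Section 11.1.2 says not to restart; Table 5 says one may.

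**Other text that might close the gap.** Section 3.3 limits only the length of interruption (12 weeks). Section 3.5.1 defines unacceptable toxicity by pointing back to 3.3. Table 5 does not refer to 11.1.2.

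**The case against.** The strongest reply is that the protocol already contains the stop. Section 11.1.2 covers both subsequent severe liver-test changes and liver failure, and the Grade 4 cell always offers discontinuation, so a site can satisfy both texts by stopping. That stands, and it rules out a stronger reading: someone might infer that Table 5 orders rechallenge, or that the protocol has no liver stop for sunitinib. It does not, and it has one. The stop is missing from the table that sites act on.

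Second, the intent may have been Grade 3 or higher. Hepatotoxicity is barred from dose reduction on recurrence, which points that way. But Table 5 has a separate Grade 4 column with its own instruction, and the same row writes ranges where it means them. If Grade 3 or higher was intended, the fix only says so.

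Third, 11.1.2 does not anchor the word for *subsequently* or grade the severity of the changes. It could refer to changes during the interruption rather than after restart, in which case resuming after full resolution would not clearly conflict. This stands in part: the inconsistency rests on the natural reading and is not a flat prohibition. The inverted order within Table 5 does not depend on it.

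Fourth, the removal sentence might cover only patients whose first event was Grade 3. That would make the stop mandatory in 3 of 5 paths instead of 5. Among those 3, a Grade 4 recurrence still leaves a restart open in 2 (37.5 and 50 mg), so the inversion remains.

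Fifth, harm needs two severe events, two resolutions and a discretionary restart, under weekly team discussion of each patient (7.4.1). This is fair, and it limits the expected number affected.

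**Conclusion.** The point holds as a safety inconsistency in a dosing table. On 37.5 or 50 mg, Table 5 requires stopping for a Grade 3 liver-test recurrence and leaves it to discretion for a Grade 4 recurrence, against the natural reading of 11.1.2. It affects 3 of 5 rule paths, of which one is open to a patient never escalated or re-escalated. The count assumes that columns follow the grade of the current event.

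The number of patients cannot be stated, because the documents give no rate for recurrent Grade 3 or 4 elevation. The 0.3% (7/2281) in 11.1.2 is liver failure, a different event. Few patients are likely to be affected.

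Three further inferences are not supported:

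- Everolimus is not handled more strictly throughout. For Grade 4 AST/ALT that resolves within 7 days, Table 8 says "everolimus should be re-started at one dose level lower. If resolution takes > 7 days, discontinue everolimus", so it too allows a restart after Grade 3 and then Grade 4. Only its liver-failure row is a contrast.
- Restarting after a first, resolved Grade 4 event without signs of liver failure is not an error.
- The removal wording does not show lost survival data or blocked cross-over. Sections 2.3.1 and 3.1.1 send unacceptable toxicity to cross-over, 3.5.2 does not list toxicity as an off-study reason, and 3.1.2 continues survival contact. No effect on PFS, power or sample size follows.

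**What to change.** 1. In the Grade 3 cell, correct ASL to AST and extend the removal sentence to recurrence at Grade ≥3.
2. Add one note that applies to both the Grade 3 and the Grade 4 non-hematologic cells: *Permanently discontinue sunitinib for any recurrent Grade ≥3 AST/ALT or bilirubin elevation, or for signs of liver failure at any grade (see 11.1.2).* Placed in the Grade 4 cell alone, it would miss Grade 3 liver failure.
3. Leave the rule for a first, resolved Grade 4 event unchanged.
4. Replace the removal-from-study wording with: *permanently discontinued from sunitinib; may cross over to everolimus if not already received and the 3.1.1 requirements are met.*

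The cost is a short amendment to one table. A few patients lose the option of a lower-dose rechallenge after a recurrent severe elevation, which 11.1.2 on its natural reading already advises against.
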